**Table 17 Guidelines for Management of Hematologic Toxicities That Occur on Days 8 and 15 of Cycle 1**

Event	Action to Be Taken
Febrile neutropenia or neutropenia with infection	
 
• Withhold obinutuzumab and venetoclax until resolution of fever and infection (as applicable) and resume at the next scheduled dose.
 
• If the patient has not already initiated G-CSF, initiate prophylactic G-CSF for current and subsequent cycles.b
 
• If the dose on Day 8 of Cycle 1 is delayed by <math>\leq 2</math> days, Day 15 of Cycle 1 should be delayed by the same number of days to retain the treatment interval for obinutuzumab.
 
• If the dose on Day 8 of Cycle 1 is delayed by <math>> 2</math> days, omit the Day 8 dose and administer the Day 15 dose as previously scheduled (if infection or neutropenic fever have resolved).
 
• If the dose on Day 15 of Cycle 1 is delayed by <math>> 2</math> days, omit the Day 15 dose and administer the next dose (Day 1 of Cycle 2) of obinutuzumab, venetoclax, and idasanutlin as scheduled (if infection or neutropenic fever has resolved).
 
• If the event is ongoing on Day 1 of Cycle 2, follow the instructions in Table 18.
 
 
Note: Obinutuzumab and venetoclax should not be withheld for asymptomatic neutropenia.

Severe thrombocytopenia a or symptomatic bleeding (irrespective of platelet count)	
 
• Withhold obinutuzumab and venetoclax until platelet count is <math>\geq 50,000</math> cells/<math>\mu\text{L}</math> with resolution of bleeding and resume at the next scheduled dose.
 
• Consider prophylactic or therapeutic platelet transfusion as appropriate
 
• In patients with HLA sensitization, HLA-compatible platelet transfusions should be administered.
 
• If the dose on Day 8 of Cycle 1 is delayed by <math>\leq 2</math> days, Day 15 of Cycle 1 should be delayed by the same number of days to retain the treatment interval for obinutuzumab.
 
• If the dose on Day 8 of Cycle 1 dose is delayed by <math>> 2</math> days, omit the Day 8 dose and administer the Day 15 dose as previously scheduled (if severe thrombocytopenia and/or symptomatic bleeding have resolved).
 
• If the dose on Day 15 of Cycle 1 is delayed by <math>> 2</math> days, omit the Day 15 dose and administer the next dose (Day 1 of Cycle 2) of obinutuzumab, venetoclax, and idasanutlin as scheduled (if severe thrombocytopenia and/or symptomatic bleeding have resolved).
 
• If the event is ongoing at Day 1 of Cycle 2, follow instructions in Table 18.
 

G-CSF = *granulocyte colony-stimulating factor*; HLA = human leukocyte antigen; QD = once a day.

a Severe thrombocytopenia is defined as a platelet count  $< 10,000$  cells/ $\mu\text{L}$  for patients who are not receiving concomitant anticoagulants or platelet inhibitors and  $< 20,000$  cells/ $\mu\text{L}$  for patients who are receiving concomitant aspirin.

b In the dose-escalation phase, prophylactic G-CSF should start after Cycle 2.

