### **5.1.8.1 Toxicities during Induction Treatment Hematologic Toxicities during Induction Treatment**

Guidelines for management of hematologic toxicities that occur during induction treatment, with the exception on Days 8 and 15 of Cycle 1 when obinutuzumab are given in Table 16. Hematologic toxicity is defined as neutropenia, anemia, or thrombocytopenia. Lymphopenia is not considered a hematologic toxicity but an expected outcome of therapy.

**Table 16 Guidelines for Management of Hematologic Toxicities That Occur during Induction Treatment (Except on Days 8 and 15 of Cycle 1)**

Event	Action to Be Taken

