Grade 3 or 4 hematologic toxicity a, b	
For patients who have had one or no prior dose reductions:
 
 
• Withhold study treatment.a
 
• Administer RBCs or platelets as required.
 
• If patient has not already initiated G-CSF, initiate prophylactic G-CSF for current and subsequent cycles.
 
• If improvement to Grade <math>\leq 2</math> or baseline within <math>\leq 14</math> days after the scheduled date for the next cycle, resume obinutuzumab or rituximab at full dose and resume idasanutlin and venetoclax at current dose.
 
• If improvement to Grade <math>\leq 2</math> or baseline 15–21 days after the scheduled date for the next cycle, resume obinutuzumab or rituximab at the full dose and resume the last escalated drug(s) at a reduced dose according to guidelines in Section 5.1.8.1 for current and subsequent cycles.
 
 
No more than three dose reductions of idasanutlin or venetoclax are allowed.
 
 
• If study treatment is withheld for <math>>21</math> days, permanently discontinue study treatment.
 
• Permanently discontinue study treatment if any of the following events occur: 
 
– Grade 3 or 4 thrombocytopenia of any duration if associated with Grade <math>\geq 3</math> bleeding
 
– Recurrent Grade 3 or 4 neutropenia if associated with fever of <math>>38^{\circ}\text{C}</math> for <math>>5</math> days) or a documented infection despite use of G-CSF and after one idasanutlin dose reduction and/or one venetoclax dose reduction or reduced schedule
 
– Recurrent Grade 4 neutropenia or thrombocytopenia lasting more than 7 days despite use of G-CSF (for neutropenia) and after one idasanutlin dose reduction and/or one venetoclax dose reduction/reduced schedule
 
 
 
 
For patients who present with recurrent Grade 3 thrombocytopenia/neutropenia in consecutive cycles:
 
If despite the use of G-CSF, for subsequent cycles, modify the venetoclax dose by reducing to next dose level or decrease the dosing schedule; reduce idasanutlin to the next dose level (see guidelines in Section 5.1.8.1).
 
For patients who have had reductions in three doses (either as single drug dose reduction or double drug reduction in the same time) or for patients who reach the lowest dose level and no further dose reduction is applicable (see Section 5.1.8):
 
 
• Permanently discontinue study treatment.
 

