### Non-Hematologic Toxicities during Induction Treatment

Guidelines for management of non-hematologic toxicities that occur during induction treatment are presented in [Table 18](#).

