**Table 18 Guidelines for Management of Non-Hematologic Toxicities**

Event	Action to Be Taken
General guidance for treatment delays, discontinuation, and resumption	
 
• If study treatment is withheld for > 21 days because of a toxicity that is attributable to study treatment, permanently discontinue study treatment.
 
• Permanently discontinue study treatment for Grade 4 events.
 
• When a treatment cycle is delayed because of toxicity resulting from any component of the regimen, all study treatment should be held and resumed together to remain synchronized.
 
• Dosing may be resumed after resolution to Grade <math>\leq 1</math> or baseline status. Resumption of dosing without complete resolution of toxicity may be considered in special circumstances after having obtained Medical Monitor agreement.
 

IRRs and anaphylaxis	
 
• Guidelines for the management of IRRs are provided in Section 5.1.1.1. In case of Grade 4 IRRs or anaphylaxis, study treatment should be permanently discontinued.
 

Clinical and laboratory TLS	
Grade 4 events:
 
 
• Permanently discontinue study treatment in the case of Grade 4 events.
 
 
Grade <math>\leq 3</math> events:
 
 
• Withhold study treatment. a
 
• Correct electrolyte abnormalities, monitor renal function and fluid balance, and administer supportive care, including dialysis as indicated.
 
• If symptoms (laboratory and clinical) have resolved completely, resume obinutuzumab or rituximab at full dose and resume venetoclax and idasanutlin at current dose.
 

New-onset neurologic manifestations suggestive of PML	
 
• Withhold study treatment. a
 
• Consult with a neurologist if PML is suspected (refer to Section 5.1.1.5 for guidance on investigations).
 
• If PML is ruled out, resume obinutuzumab or rituximab at the full dose and resume idasanutlin and venetoclax at the current dose.
 
• If PML is confirmed, permanently discontinue study treatment.
 

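### Table 17 sends cytopenias still present on Cycle 2 Day 1 to the non-hematologic table, which permanently stops Grade 4 events that Table 16 would hold and resume

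*Protocol*

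**What the plan says.** Table 17 (protocol Section 5.1.8.1) tells sites how to handle two kinds of event on Days 8 and 15 of Cycle 1. The first row is febrile neutropenia or neutropenia with infection. The second is severe thrombocytopenia, or symptomatic bleeding at any platelet count. The first row closes with "If the event is ongoing on Day 1 of Cycle 2, follow the instructions in" Table 18, and the second with "If the event is ongoing at Day 1 of Cycle 2, follow instructions in" Table 18.

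The scope of each neighbouring table is stated:

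- **Definition (Section 5.1.8.1).** "Hematologic toxicity is defined as neutropenia, anemia, or thrombocytopenia".
- **Table 16.** By its title it covers hematologic toxicity on every induction day other than Days 8 and 15 of Cycle 1.
- **Table 18.** It is introduced by "Guidelines for management of non-hematologic toxicities that occur during induction treatment are presented in" Table 18.

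**The concern.** A neutropenia or thrombocytopenia that persists to Cycle 2 Day 1 is hematologic by the protocol's own definition, and that day lies within Table 16. The printed reference nevertheless sends the site to a table written for other toxicities. Table 18 has no row for either cytopenia, so the site is left with its general guidance, including "Permanently discontinue study treatment for Grade 4 events".

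This is a stop-or-continue instruction, so a wrong reference can change what a patient receives. It can also reach the primary endpoint. Under Appendix 1, footnote ff, end-of-induction imaging is done only after at least two induction cycles. Section 6.5.1 counts a patient with no post-baseline tumor assessment as a non-responder, and Section 6.5 keeps in the analysis everyone in expansion who received one dose of any component.

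**Working it through.** No stated figure needs reproducing. The check sets the two tables side by side for the same patient, then counts what is lost.

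**1. Instructions on Cycle 2 Day 1, first event, no Grade 3 or worse bleeding**

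| Event | Table 18 (as Table 17 directs) | Table 16 (by scope) |
|---|---|---|
| Grade 4 cytopenia | Permanent stop | Withhold. Recovery to Grade 2 or lower, or baseline, within 14 days: "resume obinutuzumab or rituximab at full dose and resume idasanutlin and venetoclax at current dose". Recovery at 15–21 days: last escalated drug(s) reduced. Beyond 21 days: stop |
| Grade 3 cytopenia | "Dosing may be resumed after resolution to Grade" 1 or lower, or to baseline (earlier only if the Medical Monitor agrees); idasanutlin and venetoclax then reduced under the row for other non-hematologic toxicities, if the event is related to them (Section 5.1.8) | Same rule as for Grade 4: Grade 2 or lower, or baseline, is enough, at the current dose if within 14 days |

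Table 16's own stop rule for Grade 4 cytopenia requires a recurrent event lasting more than 7 days after a dose reduction, so a first event does not meet it.

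**2. Is Table 16 equipped for these events?** Yes. It has specific rules for neutropenia with prolonged fever or documented infection, and for thrombocytopenia with Grade 3 or worse bleeding. Those are the combinations in Table 17's two rows. Row 2 can also be entered on platelet count alone, which is a purely hematologic event.

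**3. Who is exposed?** Cycle 2 Day 1 is Day 29 of a 28-day cycle. It falls 29 − 15 = 14 days after Day 15 and 29 − 8 = 21 days after Day 8. In dose escalation, Grade 4 neutropenia or thrombocytopenia lasting more than 7 days is a DLT (for neutropenia, despite supportive care), as is Grade 3 or 4 neutropenia with documented infection (Section 3.1.2.1). A DLT in Cycles 1–2 stops treatment anyway (Sections 3.1.2 and 4.6.2). In expansion, DLBCL patients receive rituximab on Day 1 only (Table 4). That leaves mainly the FL expansion cohort, about 40 patients (Section 3.1.3).

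**4. Loss per patient stopped on Cycle 2 Day 1 (planned doses from Table 4)**

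- Cycles: 5 of 6 not given, 5/6 = 83%.
- Obinutuzumab: planned 3 + 5 = 8 infusions; 5 lost to the stop, 5/8 = 62.5%.
- Idasanutlin, Regimen A: planned 5 × 6 = 30 doses; 25 lost, 25/30 = 83%.
- Idasanutlin, Regimen B: planned 5 × 5 = 25 doses; all 25 lost.
- Under Table 16 with recovery by day 21, no cycle is dropped by the rule.

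**5. Effect on the endpoint.** The patient has received one cycle, so no end-of-induction PET-CT is scheduled. A Regimen A patient who has taken all three drugs is not replaced. A Regimen B patient would be replaced under Section 4.6.2 but still counts in the analysis under Section 6.5.

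**The case against.** The strongest objection is that Table 18 may have been intended. Its first row is headed as general guidance on delays, discontinuation and resumption, and Section 5.1.8 itself cites Table 18 for the 21-day limit on all study treatment. This reading does not hold. If that row's Grade 4 rule applied to cytopenias, it would cancel Table 16's hold-and-resume rule. A Grade 4 cytopenia starting on Cycle 2 Day 1 would be held, while the same event starting on Cycle 1 Day 15 would end treatment, and no reason is given for the difference.

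Other objections stand in part:

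- **Infection and bleeding.** These are not hematologic by definition, and Section 5.3.5.3 has an infection accompanying neutropenia recorded separately. A Grade 4 infection would stop treatment under Table 18 whatever Table 17 cites. The clean conflict is therefore a cytopenia with no governing non-hematologic component.
- **Sites may find the right rule.** Table 16's title is clear, and Section 4.6.2 lists hematologic stopping criteria separately. But Section 4.6.2 points back to Section 5.1.8, where the faulty reference sits.
- **The error leans toward caution.** It stops or delays treatment and does not permit dosing through severe cytopenia.
- **The Regimen B figure is an upper case.** Cycle 1 there is obinutuzumab alone. Section 4.6.2 lets the other drugs continue, after Medical Monitor discussion, for a patient with clinical benefit whose toxicity is solely due to one drug.
- **The cause is not established.** Section 5.1.1.2 cites Table 8 for premedication that is in Table 7, and Section 5.1.1.5 cites Table 19 for PML management that is in Table 18. Those are off by one; Table 17's reference is off by two. Uncorrected numbering is plausible, but the finding does not depend on it.

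**Conclusion.** The concern holds and should be fixed. Both Table 17 references point to the wrong table for neutropenia and thrombocytopenia. For a first Grade 4 cytopenia without Grade 3 or worse bleeding, the printed reference and the governing table give opposite instructions; for Grade 3 they differ on the recovery threshold and on dose.

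The reach is narrow: mainly FL expansion patients whose cytopenia persists to Cycle 2 Day 1 and would recover within Table 16's 21-day limit. How many there will be cannot be derived from the documents, and no effect on the complete response rate is claimed. The per-patient losses assume that the site follows the reference literally and that the single-drug exception in Section 4.6.2 is not used.

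**What to change.** In each row of Table 17, replace the reference to Table 18 with Table 16 for neutropenia or thrombocytopenia ongoing on Day 1 of Cycle 2. Add a short clause keeping Table 18 for the non-hematologic part: a separately recorded infection in the first row, and bleeding without thrombocytopenia in the second. A bare swap would leave the latter pointing to a table with no row for it.

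The cost is two corrected references, with those clauses, in the next amendment. No patients, visits or procedures are added. The table references in Sections 5.1.1.2 and 5.1.1.5 can be corrected at the same time.

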### Non-Hematologic Toxicities during Induction Treatment

Guidelines for management of non-hematologic toxicities that occur during induction treatment are presented in [Table 18](#).

**Table 18 Guidelines for Management of Non-Hematologic Toxicities**

Event	Action to Be Taken
General guidance for treatment delays, discontinuation, and resumption	
 
• If study treatment is withheld for > 21 days because of a toxicity that is attributable to study treatment, permanently discontinue study treatment.
 
• Permanently discontinue study treatment for Grade 4 events.
 
• When a treatment cycle is delayed because of toxicity resulting from any component of the regimen, all study treatment should be held and resumed together to remain synchronized.
 
• Dosing may be resumed after resolution to Grade <math>\leq 1</math> or baseline status. Resumption of dosing without complete resolution of toxicity may be considered in special circumstances after having obtained Medical Monitor agreement.
 

IRRs and anaphylaxis	
 
• Guidelines for the management of IRRs are provided in Section 5.1.1.1. In case of Grade 4 IRRs or anaphylaxis, study treatment should be permanently discontinued.
 

Clinical and laboratory TLS	
Grade 4 events:
 
 
• Permanently discontinue study treatment in the case of Grade 4 events.
 
 
Grade <math>\leq 3</math> events:
 
 
• Withhold study treatment. a
 
• Correct electrolyte abnormalities, monitor renal function and fluid balance, and administer supportive care, including dialysis as indicated.
 
• If symptoms (laboratory and clinical) have resolved completely, resume obinutuzumab or rituximab at full dose and resume venetoclax and idasanutlin at current dose.
 

New-onset neurologic manifestations suggestive of PML	
 
• Withhold study treatment. a
 
• Consult with a neurologist if PML is suspected (refer to Section 5.1.1.5 for guidance on investigations).
 
• If PML is ruled out, resume obinutuzumab or rituximab at the full dose and resume idasanutlin and venetoclax at the current dose.
 
• If PML is confirmed, permanently discontinue study treatment.
 

**Table 18 Guidelines for Management of Non-Hematologic Toxicities (cont.)**

AST, ALT, or bilirubin increase:	
Grade 4 events:
 
 
• Permanently discontinue study treatment in the case of Grade 4 events.
 
 
Grade 2 or 3 events (or <math>\geq 10 \times</math> ULN for patients with liver involvement):
 
 
• Withhold study treatment.a
 
• If improvement to Grade <math>\leq 1</math> (or <math>\leq 5 \times</math> ULN (Grade 2) for patients with liver involvement), resume obinutuzumab or rituximab and idasanutlin at full dose and resume venetoclax at next lower dosea for current and subsequent cycles per guidelines in Section 5.1.8. No more than three dose reductions of venetoclax are allowed. Patients who have had three prior dose reductions of venetoclax and/or idasanutlin should be permanently discontinued. Permanently discontinue study treatment for life-threatening liver toxicity (including Hy'sLaw cases).
 

Diarrhea	Grade 4 diarrhea: permanently discontinue study treatment.

IRR = infusion-related reaction; PML = progressive multifocal leukoencephalopathy; ULN = upper limit normal.

a Treatment delays apply to all events; dose modifications apply only to events that are considered to be related to any of the study treatment components.

b Clinical judgment should prevail, reserved for events having a significant effect on a patient's clinical situation, and upon consultation with the Medical Monitor.

**Table 18 Guidelines for Management of Non-Hematologic Toxicities (cont.)**

Event	Action to Be Taken
Diarrhea (cont.)	
Grade 2 or 3 diarrhea:
 
 
• If Grade 3 diarrhea occurs between Days 1 and 5 of the treatment cycle, withhold study treatment only if diarrhea does not improve to Grade <math>\leq 2</math> within 48 hours with appropriate treatment. After the study treatment is withheld, if diarrhea improves to Grade <math>\leq 2</math>, resume obinutuzumab or rituximab at the full dose and resume idasanutlin and venetoclax at a reduced dose according to guidelines in Sections 5.1.8.1 and 5.1.8.2 for current and subsequent cycles.
 
• If Grade 3 diarrhea is present at the time of the next planned cycle, withhold study treatment. If diarrhea improves to Grade <math>\leq 2</math>, resume obinutuzumab or rituximab at full dose and resume idasanutlin and venetoclax at a reduced dose according to guidelines in Sections 5.1.8.1 and 5.1.8.2 for current and subsequent cycles.
 
 
Management for diarrhea:
 
 
• Rule out other or concomitant causes, including, but not limited to, medications, Clostridium difficile infection, malabsorption/lactose intolerance, fecal impaction, and dietary supplements high in fiber.
 
• Initiate treatment at the time of onset.
 
• Administer loperamide 4 mg as loading dose; and up to 2 mg every 4 hours or after every unformed stool (for a maximum daily dose of 16 mg), or per institutional standard.
 
• For subsequent episodes, use 4 mg QD prophylactic loperamide 30 minutes before subsequent dosing. If diarrhea persists after 48 hours despite administration of the maximum recommended daily loperamide dose (16 mg/24 hr), second-line agents may be considered (diphenoxylate, atropine, octreotide, budesonide, or tincture of opium). Encourage patients to hydrate abundantly and self-medicate with loperamide 2 mg in the event that diarrhea recurs (up to 2 mg every 4 hours or after every unformed stool for a maximum daily dose of 16 mg), or per institutional standard.
 
• Monitor electrolyte levels closely and correct as appropriate.
 
• Administer IV fluids as clinically indicated.
 
• Upon presentation of Grade 3 diarrhea or diarrhea persists for >24 hours despite maximum recommended daily loperamide dose, exclude presence of active infections (e.g., C difficile). If present, treat infection(s), according to local guidelines.
 


IRR=infusion-related reaction; PML=progressive multifocal leukoencephalopathy; ULN=upper limit normal.

a Treatment delays apply to all events; dose modifications apply only to events that are considered to be related to any of the study treatment components.

b Clinical judgment should prevail, reserved for events having a significant effect on a patient's clinical situation, and upon consultation with the Medical Monitor.

**Table 18 Guidelines for Management of Non-Hematologic Toxicities (cont.)**

Event	Action to Be Taken
Nausea and vomiting	
Grade 4 vomiting:
 
 
• Permanently discontinue study treatment.
 
 
Grade 1, 2, or 3 vomiting or nausea:
 
 
• Consider prophylaxis with second-generation anti-emetics like palonosetron, ondansetron, or granisetron.
 
• If vomiting occurs within 15 minutes of taking idasanutlin and/or venetoclax, and all expelled tablets are still intact, another dose may be given and the second dose noted in the drug log. Otherwise, no replacement dose is to be given (see Sections 5.1.8.1 and 5.1.8.2).
 

Dermatologic toxicity	Permanently discontinue rituximab in the event of Stevens-Johnson syndrome or toxic epidermal necrolysis.

Other non-hematologic toxicities (i.e., not described above), excluding alopecia
 
Grade 3 or 4
 
Grade 2
	
Grade 4 events
 
 
• Permanently discontinue study treatment.
 
 
Grade 3 events
 
 
• Withhold study treatment.a
 
 
If improvement to Grade <math>\leq 1</math> or baseline, resume obinutuzumab or rituximab at the full dose and resume idasanutlin and venetoclax at reduced (Section 5.1.8) dosea for subsequent cycles. No more than three dose reductions of idasanutlin or venetoclax are allowed.
 
For patients who have had three prior dose reductions (either as a single drug dose reduction or double drug reduction in the same time) or for patients who reach the lowest dose level and no further dose reduction is applicable (See Section 5.1.8):
 
 
• Permanently discontinue study treatment.
 
 <hr/> 
 
• Withhold study treatment.a, b
 
• If improvement to Grade <math>\leq 1</math> or baseline, resume obinutuzumab or rituximab at the full dose and resume idasanutlin and venetoclax at the current dose.
 

IRR=infusion-related reaction; PML=progressive multifocal leukoencephalopathy; ULN=upper limit normal.

a Treatment delays apply to all events; dose modifications apply only to events that are considered to be related to any of the study treatment components. Toxicities that occur during the cycle and subside prior to the next cycle should not trigger the suggested dose modifications.

b Clinical judgment should prevail, reserved for events having a significant effect on a patient's clinical situation, and upon consultation with the Medical Monitor.

